### **Therapeutic Exercises**

All therapeutic exercises will be instructed, supervised and progressed by physical therapists at the Meadowmont Physical Therapy Clinic. Over twelve 45-minute sessions that will take place in a 4-week period. The goal will be to complete at least 1 session per week with a 4 session per week maximum. The study team will assist with scheduling the first physical therapy session, while Meadowmont Physical Therapy personnel will schedule all additional sessions. The study team will check in with Meadowmont Physical Therapy personnel and the patient to ensure that the patients are being scheduled at the correct frequency.

### **Muscle Stretches**

Quadriceps Stretch- Patient lays prone on the table and the physical therapist moves the ankle towards the gluteal muscles. Three stretches are held for 20 seconds in both limbs.

Hamstring Stretch- Patient sits at the edge of chair with knee straight, heel contacting the ground, and ankle dorsi flexed. The participant will bend at the hips until a stretch is felt in the hamstring. Three stretches are held for 20 seconds in both limbs.

Calf Stretch- Patient will stand in a staggered stance with palms against wall. Heel will be push to ground with knee flexed to 30 degrees and knee straight at 0 degrees. Three stretches are held for 20 seconds in both limbs.

### **Strengthening Exercises**

Quadriceps Sets- Patients will be positioned on the table supine or seated with knees extended. Patients will be instructed to contract their quadriceps in order to fully extend the knee with the goal of lifting their heel off of the table. Tactile feedback can be provided to the posterior knee (instructing patient to put pressure on the therapist's hand) or to the quadriceps in a manner to cue the patient on which muscle to contract. Each repetition of should be held for 5 seconds.

Short Arc Quadriceps- Patients will be positioned on the table supine or seated with a bolster under the knee (half to full foam roller based on patient size). The knee should be in approximately 20-30° of knee flexion. Patients will be instructed to contract their quadriceps in order to fully extend the knee with the goal of lifting their heel off of the table and finishing with a fully extended knee. Tactile feedback can be provided to the posterior knee (instructing patient to put pressure on the therapist's hand) or to the quadriceps in a manner to cue the patient on which muscle to contract.

Straight Leg Raises (Flexion)- Patients will be positioned on the table supine with knees extended. The contralateral limb will be in knee flexion in order to create a ~45° angle at the hip. Patients will be instructed to

perform an initial quadriceps set (1 second hold) and keep knee extended while lifting the involved limb and heel off the table to ~45° angle. The patients will lower the limb back to the table slowly over a 2 second period. Tactile feedback can be provided to the quadriceps in a manner to cue the patient on which muscle to contract. If needed- the physical therapist may actively assist the first several repetitions by lifting the heel in the correct plane of motion. Cuff weights can be added to the ankle and the DAPRE system will be used to progress weight.

**Straight Leg Raises (Abduction)-** Patients will be positioned on the table side-lying on the uninvolved limb with knees extended. The uninvolved limb should be positioned with the hip and the knee flexed to 90°. The involved hip should be abducted to ~45° while keeping the knee extended. The patients will lower the limb back to the table slowly over a 2 second period. Tactile feedback can be provided to the gluteus medius in a manner to cue the patient on which muscle to contract. If needed- the physical therapist may actively assist the first several repetitions by lifting the heel in the correct plane of motion. Cuff weights can be added to the ankle and the DAPRE system will be used to progress weight.

**Step-ups-** Patients will be instructed to stand facing the step at a distance of about 6-inches. Patients will then be asked to put the involved limb on the step and contract quadriceps and hip musculature to bring both limbs onto the step. After pausing for one second the patient will be instructed to step off the back of the step with the uninjured limb in an lower the body slowly to the ground with the control of the muscles in the injured limb that is still on the step. Both feet should return to the floor before another repetition is started. Patients should progress to the next phase if they complete two sets in a row without increased knee pain and body mechanics are deemed within normal by the therapist. Patients will progress from the 4" to the 6" and 8" step and will further progress by holding a weight in the ipsilateral hand. Weights should increase in 5lb increments.

**Long Arc Knee Extension-** Knee extension will be performed seated on a table with knees flexed. The lever arm will be adjusted to have the foam pad make contact with the tibia approximately one-third of the way up the distal tibia. Patients will be instructed to extend the knee until full extension is achieved and patients "squeeze the quadriceps" for a 1-2 second hold. If patients experience knee pain the therapist should adjust the arc of knee extension motion to a point that minimizes pain. The weight should then be lowered to the resting position in approximately 2-3 seconds. Weights can be added to the table and the DAPRE system will be used to progress weight.

**Long Arc Knee Flexion-** Knee flexion will be performed seated on a table with knees extended. The lever arm will be adjusted to have the foam pad make contact with the leg approximately one-third of the way up the distal calf on the posterior side. Patients will be instructed to flex the knee until ~90° is achieved and patients "squeeze the hamstrings" for a 1-2 second hold. If patients experience knee pain the therapist should adjust the arc of knee flexion motion to a point that minimizes pain. The weight should then be lowered to the resting position in approximately 2-3 seconds. Weights can be added to the table and the DAPRE system will be used to progress weight.

**Heel Raises –** Patients will stand next to a plinth and be allowed to use the plinth for balance. They will be instructed to raise their heels off the ground over a 2 second period until they are on their toes. The patients will be instructed to hold this position for 2 seconds and lower slowly over a two second period. Patients should progress to the next phase if they complete two sets in a row without increased knee pain and body mechanics are deemed within normal by the therapist. The patients can be progress to one limb and then by using weight in the contralateral hand (increasing in 5lb increments).

**Ball Squats-** The physical therapist will determine the appropriate sized physio-ball to be used in this exercise based on the size of the patient. The physio-ball will be placed at the lumbar spine of each patient between their back and the wall. The patient will keep arms at their side or crossed over the chest and their feet shoulder width apart and in front of them enough that during the squat the knees do not move anterior to the toes. The patients will squat as far as they feel comfortable aiming for between ~45 to 90° of knee flexion. The

concentric and eccentric phases of the exercise should be controlled and last 3-4 seconds in each direction with a 1-2 second hold at maximum knee flexion.

## Balance Exercises

Balance exercises will be performed with the following progressions. Patients will be supervised by a physical therapist and will perform balance exercises next to a wall, table or within a doorway to decrease risk of falling during the exercise.

## Balance Progressions

### Single Limb Stance Progression

\*\*\*Stance (3x 30s): *Progress when there are no touch downs in all 3 sets*

Level -2: Double Limb firm surface, eyes Open

Level -1: Double Limb firm surface, eyes Closed

Level 1: Single limb firm surface, eyes open

Level 2: Single limb firm surface, eyes open, **perturbation**

Level 3: Single limb firm surface, eyes **closed**

Level 4: Single limb firm surface, eyes closed, **perturbation**

Level 5: Single limb **foam** surface, eyes open

Level 6: Single limb foam surface, eyes open, **perturbation**

Level 7: Single limb foam surface, eyes **closed**

Level 8: Single limb foam surface, eyes closed, **perturbation**

### 3.g.1 Randomization

Individuals who screen into the study and complete baseline testing will be randomized to one of 3 groups. Participants will be randomized into an intervention group before meeting the patient at the clinic but following a confirmation phone call. The confirmation phone call will occur 72- 24 hours prior to the first physical therapy appointment. The purpose of the confirmation phone call is to minimize the risk that patients drop out of the study prior to being randomized to a group. After screening, patients will be stratified to one of four strata based on CAR (low < 80%, High  $\geq$  80%; Low Kellgren-Lawrence 2, High Kellgren-Lawrence 3 and 4). A separate blocked randomized list (block of 6) will be created by [name] for each strata. A set of opaque sealed envelopes will contain the randomized group assignment for each participant. [name] will have the randomized lists in case cross-referencing is ever needed in the future. The principal investigator will check with [name] for each of the first 10 participants that are randomized from each list match the assignment from the envelopes, and at every 5th randomized participant for the rest of the study. During assembly of the envelopes a 5th strata list will be developed and cross referenced immediately after assembly as a quality control measure.

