Informed Consent & Scheduling	[name] [name] [name]	These personnel will be in charge of consenting each patient, explaining the study to each participant and acquiring written informed consent from each participant. [name] and [name] will schedule patients for: 1) screening/baseline sessions, 2) the first physical therapy session (all other physical therapy sessions will be scheduled by the the clinic staff), 3) follow-up test one, and 4) follow-up test two.
Screening	[name] [name] [name] [name]	Screening will consist of central activation ratio and WOMAC score testing.
Collection of Data (Baseline and Follow-up Measures)	[name] [name]	These follow-up tests will be conducted by only the blinded investigators at baseline, follow-up one (4 weeks) and follow-up two (8-weeks).
Education on TENS unit and Sham TENS with Patients (Available to answer questions throughout study)	[name] [name] [name]	These investigators will be unblinded and will be in charge of teaching patients how to utilize the active TENS and Sham TENS units immediately prior to the first physical therapy session. Additionally, phone numbers for [name] and [name] will be provided if further assistance is needed.
Delivery of Physical Therapy Intervention	[name] [name] [name] [name] [name] [name]	Patients will be scheduled to work independently with one of these clinicians. All clinicians will conduct therapeutic exercises according to the guidelines provided in g.1 .
Study Compliance & Accountability	[name]	[name] will evaluate study compliance for 1) randomization, follow-up testing, IRB Compliance, and compliance of treatment protocols as described in section 3.m
Randomization of Patients	[name] [name] [name]	The randomization scheme will be developed by [name] and [name] will determine each patient's group from a sealed envelopes. [name] will be unblinded and in charge of the randomization lists.
Data Entry, Error Identification and Correction	[name] [name] [name]	[name] and [name] will perform double data entry. [name] will calculate means and standard deviations separately for all outcomes measures. [name] will determine were potential errors are found and [name] (Blinded

		Investigator) will be consulted to determine the correct outcome measure.

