We will aim to ensure that subject selection is equitable and all relevant demographic groups have access to study participation by contacting (via initial letter and telephone call) all patients who meet inclusion / exclusion criteria, regardless of demographic characteristics. We have also aimed to produce recruitment and intervention materials that are appropriate for individuals with low literacy or education levels. We will continue to recruit patients until we reach our sample size goal of N=90.

Screening questionnaire data will be entered directly into the study database via the software package Epi Info. We will have paper copies of screening questionnaires that may be used in cases of computer network failure. We anticipate this will be rare. However, if paper forms are needed, data will then be entered into Illume as soon as possible. Any paper copies that are used will be stored in the subject's individual study folders, which are kept in a locked file cabinet in a locked office in the neuromuscular Research Laboratory.

The list of potential study participants, based on medical record review, will be transferred into a secure computerized tracking database. Likewise, subject data for all subjects enrolled in the study will be entered into a secure computerized enrollment log. This data will be accessible only to study personnel needing access to fulfill their study related duties.

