### Strata

Strata A = Low CAR, Low Kellgren- Lawrence

Strata B =High CAR, Low Kellgren- Lawrence

Strata C= Low CAR, High Kellgren- Lawrence

Strata D= High CAR, High Kellgren- Lawrence

The unblinded investigator, [name], will pull the next envelope from the appropriate strata after the patient visit is confirmed and as close to the visit as possible to allow for adequate setup time. Before randomizing a participant the investigator will confirm that a cancelation email or message has been received. Again the goal is to avoid randomizing a participant that eventually drops out of the study to a treatment group. Following randomization the envelop will be shredded by the unblinded investigator.

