### 3.h Blinding and Unblinding

The current study is a double-blinded randomized controlled trial, where the investigators evaluating study outcomes as well as patients in the TENS+TE and Sham TENS + TE groups will be blinded. There will be no effort to blind patients in the control or TE only group.

The unblinded personnel in the study will be [name] (in charge of back-up randomizations lists), [name] (in charge of screening, randomization and scheduling), [name] (in charge of screening, randomization and scheduling), and [name] (in charge of initial randomization and study analysis). All efforts will be made to maintain the blinding of all other study personnel collecting data as well as the patients in the study. We will assess blinding of patients and study personnel at the end of the study to determine efficacy of the blinding procedures. We will not unblind any of the blinded personnel until after the study has been completed and all outcome measures for all patients have been analyzed and imputed into databases.

We will unblind the patients if: 1) they sustain a medical condition that requires that they know their group assignment or 2) they request the information in writing following the completion of the project in that all outcome measures for all patients have been analyzed and imputed into databases.

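### A fixed, disclosed block size of 6, with screening and randomisation duties held by the same unblinded staff, lets about 16–20% of assignments be known before randomisation

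*Combined protocol and SAP*

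**What the plan says.** Section 3.g.1 sets the scheme: "Individuals who screen into the study and complete baseline testing will be randomized to one of 3 groups". It continues: "After screening, patients will be stratified to one of four strata based on CAR", with Kellgren-Lawrence grade as the second factor. For each stratum, "A separate blocked randomized list (block of 6) will be created". Concealment is by envelope: "A set of opaque sealed envelopes will contain the randomized group assignment for each participant".

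Under Strata, one unblinded investigator "will pull the next envelope from the appropriate strata after the patient visit is confirmed". Section 3.g.1 places the confirmation call 72 to 24 hours before the first physical therapy appointment, after consent, screening and baseline testing.

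Section 3.h lists four unblinded people and describes two of them with the same words: "in charge of screening, randomization and scheduling". The roster in section 3.c adds a further source of knowledge about assignments: "These investigators will be unblinded and will be in charge of teaching patients how to utilize the active TENS and Sham TENS units". It also gives patients the telephone numbers of two staff for later help.

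Section 3.t keeps the manual, and so the block size, open to all study staff. Nothing in the document withholds the block size from those who screen, or separates screening and booking from knowledge of past assignments.

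**The concern.** Opaque envelopes stop someone from reading an assignment. They do not stop someone from counting what is left in a block of known size. Envelopes are drawn in order within a stratum, and the staff who draw them or teach the devices know what came before. As a block fills, the next assignment becomes easier to guess and finally certain.

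What matters is whether a person with that knowledge can affect who comes next. The section 3.h role labels put screening and scheduling with two such people. Because the envelope is pulled late, the order in which confirmed patients reach it depends on booking. Someone who knows or strongly suspects the next assignment could move a booking forward or back, or could encourage or discourage an eligible patient before randomisation. Either would make the arms differ in ways that randomisation is meant to prevent and that the measured baseline variables need not show.

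**Working it through.** The plan gives no predictability figure, so there is none to reproduce.

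Inputs:
- Block size 6, three arms, four separate lists (section 3.g.1).
- Total sample size 90: "We will continue to recruit patients until we reach our sample size goal of N=90" (section 3.e.1).
- Assumption: 1:1:1 allocation, so two per arm in each block. The ratio is not stated.
- Assumption: the observer knows the block size and every earlier assignment in the stratum.

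**One complete block.** There are 6!/(2!·2!·2!) = 90 equally likely orders. An assignment is certain when only one arm is left.
- Position 6 is always certain.
- Position 5 is certain when the last two places hold the same arm: 3 × 6 = 18 of 90 orders, or 1/5.
- Positions 1 to 4 are never certain, because at least three places remain and no arm fills more than two.

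| Position | Certain | At least one arm excluded | Best guess right |
|---|---|---|---|
| 1 | 0 | 0 | 2/6 = 0.333 |
| 2 | 0 | 0 | 2/5 = 0.400 |
| 3 | 0 | 0.2 | 2/4 = 0.500 |
| 4 | 0 | 0.6 | 0.4 × 1/3 + 0.6 × 2/3 = 0.533 |
| 5 | 0.2 | 1 | 0.2 × 1 + 0.8 × 1/2 = 0.600 |
| 6 | 1 | 1 | 1.000 |
| Sum | 1.2 | 2.8 | 3.367 |
| Sum / 6 | 20.0% | 46.7% | 56.1% |

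Listing all 90 orders confirms the first column: 108 of 540 positions are certain, or 20.0%. Chance guessing is right 33.3% of the time.

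**The whole trial.** The split of 90 over the strata is not given, so all splits were checked.
- Highest: all blocks complete, for example 18/24/24/24. That is 15 blocks × 1.2 = 18.0 certain, or 20.0%.
- Lowest: for example 22/22/23/23. That is 12 complete blocks × 1.2 = 14.4, plus 0.2 for each of the two strata that stop at position 5, giving 14.8, or 16.4%.

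For 22/22/23/23 the other two figures also fall a little:
- At least one arm excluded: (12 × 2.8 + 2 × 0.8 + 2 × 1.8)/90 = 38.8/90 = 43.1%.
- Best guess right: (12 × 3.367 + 2 × 1.767 + 2 × 2.367)/90 = 48.7/90 = 54.1%.

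**Effect of varying the block size.** This was simulated with 4,000 lists of 24, for an observer who knows the set of sizes but not their order.

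| Sizes | Certain | Best guess right |
|---|---|---|
| 6 only | 20.0% | 56.2% |
| 3 and 6 | 8.0% | 57.3% |
| 6 and 9 | 4.8% | 53.2% |
| 3, 6 and 9 | 3.2% | 54.6% |

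The first row agrees with the exact result. An observer who knows nothing of the sizes has no certain assignments. Varying the size therefore removes most of the certainty but little of the guessing advantage, and mixing 3 with 6 makes guessing slightly easier than 6 alone.

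**The case against.** The case for the plan has several parts.

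- **Timing.** A reader might infer that one assignment in five is predictable before enrolment. The documents do not support that. Consent comes first, the stratum is known only once the central activation ratio (CAR) and Kellgren-Lawrence grade are both available, and the envelope follows baseline testing and the confirmation call. The claim must be limited to predictability before randomisation, given the stratum.
- **Knowledge.** The 20% figure needs complete blocks and full knowledge of four interleaved lists. If the two randomising staff do not share assignments, each knows less. This stands, and makes 16–20% the figure for a fully informed observer.
- **The CAR cut-offs.** It is tempting to say that a screener could push a patient across the 90% entry limit or the 80% stratum limit. That route is weak. CAR is collected with an automated trigger (section 3.i.2) and Kellgren-Lawrence grade is supplied on request from stored radiographs (External Data). Under section 3.m, eligibility is confirmed before randomisation for the first 10 patients, and files of randomised patients are then checked monthly.
- **Who does what.** Names are removed, the roster lists four screeners, and Strata describes one envelope-puller. That one person both tests a patient and opens that patient's envelope is an inference from the role labels in section 3.h.

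The checks of envelopes against lists in sections 3.g.1 and 3.m do not answer the point. They detect a wrong assignment, but not an eligible patient steered towards, or away from, a correct one. The booking and encouragement routes remain open.

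**Conclusion.** The concern holds as a weakness in allocation concealment. With a fixed and disclosed block of 6, a person who knows the earlier assignments in a stratum can be certain of 14.8 to 18 of 90 assignments before randomisation. In complete blocks that person can exclude an arm for about 47% and guess correctly about 56% of the time. These figures rest on an assumed 1:1:1 ratio and on full knowledge of earlier assignments.

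Two further readings go too far. The documents show an opportunity for selection bias; they do not show that it occurred or how large its effect would be. Nor would varied block sizes alone repair the design, since guessing would stay at about 53–55%.

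The arithmetic is firm. What is less certain is how far the duties overlap for any one patient, because the document gives roles rather than a per-patient division of work.

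**What to change.** 1. **Separate the knowledge (main protection).** Among the staff already named, whoever screens and schedules patients should neither open envelopes nor teach the devices or take device calls, so that they do not learn past assignments. Moving only the envelope-opening is not enough, because teaching the devices reveals the same information. Align the roster in section 3.c, the Strata text and section 3.h with this division.
2. **Vary and conceal the block sizes.** Generate each of the four lists with randomly ordered sizes, for example 6 and 9. Delete the size from section 3.g.1 and hold the sizes only with the list-maker. State the allocation ratio in the same section.

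The cost is four regenerated lists, edits to three places for the roles and one for the block size, and a small reallocation of duties. Possible imbalance at the end of a list rises slightly: two arms can differ by at most 2 in an unfinished block of 6 and by 3 in a block of 9. Over four strata the worst case is therefore 4 × 3 = 12 rather than 4 × 2 = 8.
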